Section 1.1. Synopsis	Added the safety-related secondary objective and endpoints Modified to state that the dosing will occur twice on Day 0 and Day 90 (-5 to +10 days)	Changes to study design and for clarification
Section 1.3. Schedule of Activities (SoA)	Changed the visit tolerance interval from ± 5 to “-5 to +10” for Visit 6 Changed the follow-up visit V801 to on-site for all sites including the US Clarified that the second PK sample will be taken 4-12 hr post-dose (minimum 2 hr)	To give more flexibility to participants with COVID infection Since ECG is required at V801, an on-site ECG is preferable Clarified the timing of the second PK sample
Section 3 Objectives, Endpoints, and Estimands	Added the safety-related secondary objective and endpoint For intercurrent events, added language to indicate that the excluded medications or new initiation of any lipid-lowering drugs are handled by hypothetical strategies	Added safety objective to align with trial title Clarification for the estimand
Section 4.1. Overall Design	Modified dosing at Day 90 (-5 to +10 days)	To give more flexibility to participants with COVID infection

Section 5.1 Inclusion Criteria	
Modified age limit from 40 to 18 years of age for IC #1
 
Modified the lower limit of fasting TG to 150 mg/dL (1.69 mmol/L) for IC #2
 
Modified the cut-off for fasting LDL-C to 70 mg/dL (1.81 mmol/L) for IC #3
 
Added non-HDL-C \geq130 mg/dL (3.36 mmol/L) as IC #51
	To include a broader population that could benefit from this therapy
Section 5.2. Exclusion Criteria	
Modified EC #31 so that anemia will need to be clinically relevant at the discretion of the investigator for the participant to be excluded
 
Deleted the word “supine” from EC #34
	
To limit exclusion only to clinically relevant anemia.
 
For consistency with protocol Section 8.2.2

Section 6.1. Study Intervention(s) Administered	Modified to state that each injection should be delivered into separate quadrants when multiple injections are needed	To provide general advice in case of multiple injections
Section 10.2.1. Laboratory Samples Obtained at the Time of as Systemic Hypersensitivity Event	Only plasma samples will be collected to test the LY3561774 concentrations	Correction of the sample type
Throughout the document	Minor editorial and format changes	For clarity

Table of Contents

1.	Protocol Summary	8
1.1.	Synopsis	8
1.2.	Schema.....	11
1.3.	Schedule of Activities (SoA).....	12

1.1. Synopsis

Protocol Title:

A Phase 2, Randomized, Double-Blind, Placebo-Controlled Study to Investigate the Efficacy and Safety of LY3561774 in Adults with Mixed Dyslipidemia

Brief Title:

Efficacy and Safety of LY3561774 Compared with Placebo in Adults with Mixed Dyslipidemia

Rationale:

Residual cardiovascular risk is still high, despite the current standard of care that includes maximally tolerated statin. Studies show that a reduction in circulating biomarkers, such as non-HDL-C and apolipoprotein B (ApoB), are associated with a reduction in major cardiovascular events.

This study aims to investigate the impact of LY3561774 on surrogate biomarkers of major cardiovascular events in participants with mixed dyslipidemia. This is the first Phase 2 study and data from this study will inform dose decisions for the clinical development of LY3561774.

Overall design:

This is a Phase 2, randomized, double-blind, placebo-controlled study to investigate the efficacy and safety of LY3561774 in adults with mixed dyslipidemia.

The duration of the study is 270 days with a follow-up visit for some participants at Day 360.

Brief Summary:***Screening***

Interested participants will sign the appropriate informed consent document(s) prior to completion of any procedures.

The investigator will review symptoms, risk factors, medical history, concomitant medications and other inclusion and exclusion criteria prior to any diagnostic procedures. If the participant is eligible after this review, then the site will perform the diagnostic procedures to confirm eligibility.

Double-blind treatment and assessment period

This part of the study has 11 visits. The two visits after randomization will occur about 15 days apart and the remaining visits occur about 30 days apart.

This is the general flow during the treatment and assessment period:

- Complete MRI at any date prior to randomization
- Complete baseline procedures and sample collection
- Participants are randomly assigned to an intervention group, and
- Participants complete all visit procedures including efficacy assessments, safety monitoring, study intervention dosing, and post-dosing sample collection.

Safety follow-up

If a participant's ApoB levels do not return to $\geq 80\%$ of baseline on Day 270, then they will continue to the follow-up visit at Day 360.

If a participant's ApoB levels return to $\geq 80\%$ of baseline on Day 270, then Day 270 is their last study visit.

Objectives, Endpoints, and Estimands:

Objectives	Endpoints
Primary	
To evaluate if LY3561774 is superior to placebo for the treatment of mixed dyslipidemia in adults.	Percent change from baseline at Day 180 for ApoB.
Secondary	
Compare the clinical response of LY3561774 to placebo.	Percent change from baseline at Day 180 for 
 • ANGPTL3 • LDL-C • HDL-C • Non-HDL-C, and • Triglycerides.
	Percent change from baseline at Day 270 for 
 • ANGPTL3 • Non-HDL-C • LDL-C • HDL-C • ApoB, and • Triglycerides.
Characterize the pharmacokinetics (PK) of LY3561774.	Plasma concentrations of LY3561774.
Compare the effect of LY3561774 to placebo on safety endpoints.	Frequency of treatment-emergent adverse events.

Objectives	Endpoints
To describe the safety of LY3561774 in participants with mixed dyslipidemia.	Summary of safety data, including number and incidence of 
 • TEAEs • SAEs, and • Discontinuations due to AEs.

Abbreviations: AE = adverse event; ANGPTL = angiotensin-like; Apo = apolipoprotein; HDL-C = high-density lipoprotein-cholesterol; LDL-C = low-density lipoprotein cholesterol; SAE = serious adverse event; and TEAE = treatment emergent adverse event.

Estimands

The primary clinical question of interest is

What is the treatment difference in ApoB percent change from baseline after 180 days of treatment in participants who meet the inclusion criteria and would have completed the treatment period?

The same estimand for the primary objective will be used for the secondary clinical response endpoints.

Unless specified otherwise, safety assessments will be guided by an estimand comparing safety of LY3561774 doses with placebo irrespective of adherence to study intervention, including data collected during the treatment period and safety follow-up.

Number of Participants:

Approximately 175 participants will be randomly assigned in a 2:1:2:2 ratio to placebo: LY3561774 100 mg:400 mg:800 mg. Assuming a 20% dropout rate, this results in approximately 20 completers for 100 mg group and 40 completers per arm for the rest of the groups.

Intervention Groups and Duration:

The planned treatment arms are

- 100 mg LY3561774 or placebo
- 400 mg LY3561774 or placebo, and
- 800 mg LY3561774 or placebo.

Intervention administration is by subcutaneous injection.

Dosing will occur twice during the study on Day 0 and Day 90 (-5 to +10 days).

Data Monitoring Committee: No

1.2. Schema

1.3. Schedule of Activities (SoA)

Screening

If screening takes longer or shorter than 45 days to complete, it will not be considered a protocol deviation.

Remote visits

Visits noted in the SoA are eligible to be conducted remotely at the direction of the sponsor, according to local laws and regulations. Remote visits may be by telephone, IT-assisted virtual visit, mobile healthcare, at a local laboratory, or a combination thereof.

Safety follow-up

If a participant’s ApoB levels do not return to $\geq 80\%$ of baseline on Day 270, then the participant will continue to the follow-up visit at Day 360.

If a participant’s ApoB levels return to $\geq 80\%$ of baseline on Day 270, then Day 270 is their last study visit.

Study J3F-MC- EZCB(e)	Screening	Double-Blind Treatment and Assessment												Follow-up	Comments	
		1	2	3	4	5	6	7	8	9	10	11	12			ED
Remote Visits			X	X	X		X	X		X	X					V801 on-site for all sites including the US
Visits	1	2	3	4	5	6	7	8	9	10	11	12	ED	801	ED = early discontinuation.	
Days from randomization	-45	0	15	30	60	90	120	150	180	210	240	270	—	360		
Visit interval tolerance (days)		—	± 3	± 3	± 3	-5 to +10	± 7	—	± 7	Visit 1 procedures may be conducted over more than 1 day if all activities are completed within the allowable visit tolerance.						
Fasting Visit	X	X	X	X	X	X	X	X	X	X	X	X	X	X	Participants should not eat or drink anything but water for 8 hours before the visit. If a participant arrives not fasted, schedule the laboratory draw for another date.	
Procedures																
Informed consent	X														The ICF must be signed before any protocol-specific tests/procedures are performed. See Section 10.1.3, for additional details.	

Study J3F-MC- EZCB(e)	Screening	Double-Blind Treatment and Assessment											Follow-up	Comments	
Remote Visits			X	X	X		X	X		X	X				V801 on-site for all sites including the US
Visits	1	2	3	4	5	6	7	8	9	10	11	12	ED	801	ED = early discontinuation.
Days from randomization	-45	0	15	30	60	90	120	150	180	210	240	270	—	360	
Visit interval tolerance (days)		—	±3	±3	±3	-5 to +10	±7	±7	±7	±7	±7	±7	—	±7	Visit 1 procedures may be conducted over more than 1 day if all activities are completed within the allowable visit tolerance.
Fasting Visit	X	X	X	X	X	X	X	X	X	X	X	X	X	X	Participants should not eat or drink anything but water for 8 hours before the visit. If a participant arrives not fasted, schedule the laboratory draw for another date.
Inclusion and exclusion criteria, review and confirm	X	X													Confirm inclusion and exclusion criteria prior to randomization and administration of first dose of study intervention.
Demographics	X														Includes ethnicity (where permissible), year of birth, sex, and race.
Preexisting conditions and medical history	X														Collect all ongoing conditions and relevant past surgical and medical history including history of premature CV disease.
Prespecified medical history (indication and history of interest)	X														Additional data for the indication and comorbidities of interest.
Substance use (alcohol)	X	X	X	X	X	X	X	X	X	X	X	X	X	X	
Concomitant medications	X	X	X	X	X	X	X	X	X	X	X	X	X	X	

Study J3F-MC- EZCB(e)	Screening	Double-Blind Treatment and Assessment											Follow-up	Comments	
		1	2	3	4	5	6	7	8	9	10	11			12
Remote Visits			X	X	X		X	X		X	X				V801 on-site for all sites including the US
Visits	1	2	3	4	5	6	7	8	9	10	11	12	ED	801	ED = early discontinuation.
Days from randomization	-45	0	15	30	60	90	120	150	180	210	240	270	—	360	
Visit interval tolerance (days)		—	±3	±3	±3	-5 to +10	±7	±7	±7	±7	±7	±7	—	±7	Visit 1 procedures may be conducted over more than 1 day if all activities are completed within the allowable visit tolerance.
Fasting Visit	X	X	X	X	X	X	X	X	X	X	X	X	X	X	Participants should not eat or drink anything but water for 8 hours before the visit. If a participant arrives not fasted, schedule the laboratory draw for another date.
Adverse events (AEs)	X	X	X	X	X	X	X	X	X	X	X	X	X	X	Any events that occur after signing the informed consent are considered AEs as defined in Section 10.3. If an injection-site reaction occurs, collect an additional unscheduled immunogenicity and PK sample (Section 8.3.4).
Physical Evaluations															
Height	X														Participant should remove shoes.
Weight	X					X			X			X	X	X	
Vital signs	X	X	X	X	X	X	X	X	X	X	X	X	X	X	Includes blood pressure and pulse rate. May repeat measure once. Measure after participant has been sitting at least 5 minutes and before ECG tracing and collection of blood samples for laboratory testing.
Physical examination	X											X	X		See Section 8.2.1. The complete physical examination excludes pelvic, rectal, and breast examinations, unless clinically indicated.

Study J3F-MC- EZCB(e)	Screen ing	Double-Blind Treatment and Assessment											Follow- up	Comments	
				X	X	X		X	X		X	X			
Remote Visits			X	X	X		X	X		X	X				V801 on-site for all sites including the US
Visits	1	2	3	4	5	6	7	8	9	10	11	12	ED	801	ED = early discontinuation.
Days from randomization	-45	0	15	30	60	90	120	150	180	210	240	270	—	360	
Visit interval tolerance (days)		—	±3	±3	±3	-5 to +10	±7	±7	±7	±7	±7	±7	—	±7	Visit 1 procedures may be conducted over more than 1 day if all activities are completed within the allowable visit tolerance.
Fasting Visit	X	X	X	X	X	X	X	X	X	X	X	X	X	X	Participants should not eat or drink anything but water for 8 hours before the visit. If a participant arrives not fasted, schedule the laboratory draw for another date.
Symptom- directed physical assessment		X		X	X	X	X	X	X	X	X			X	Performed by qualified personnel per local regulations based on participant status and standard of care.
Single 12-lead ECG (local)	X					X			X			X	X	X	Collect at least 30 minutes prior to collection of blood samples for laboratory testing, including PK samples. Participants should be supine for approximately 5 to 10 minutes before ECG collections and remain supine but awake during the ECG collection. ECGs may be repeated at the investigator’s discretion at any visit.
Schedule MRI	X														Schedule MRI prior to randomization for applicable participants who meet screening inclusion and exclusion criteria.
MRI		X							X				X		Performed for the quantification of hepatic fat. See Section 8.2.4. The participant must fast for at least 6 hours prior to the MRI. If they did not fast, schedule MRI for another date prior to randomization.

Study J3F-MC- EZCB(e)	Screening	Double-Blind Treatment and Assessment											Follow-up	Comments	
		1	2	3	4	5	6	7	8	9	10	11			12
Remote Visits			X	X	X		X	X		X	X				V801 on-site for all sites including the US
Visits	1	2	3	4	5	6	7	8	9	10	11	12	ED	801	ED = early discontinuation.
Days from randomization	-45	0	15	30	60	90	120	150	180	210	240	270	—	360	
Visit interval tolerance (days)		—	±3	±3	±3	-5 to +10	±7	±7	±7	±7	±7	±7	—	±7	Visit 1 procedures may be conducted over more than 1 day if all activities are completed within the allowable visit tolerance.
Fasting Visit	X	X	X	X	X	X	X	X	X	X	X	X	X	X	Participants should not eat or drink anything but water for 8 hours before the visit. If a participant arrives not fasted, schedule the laboratory draw for another date.
															Visit 2: Perform MRI at any day prior to randomization. ED Visit: if ED Visit is prior to Visit 9, then conduct MRI. If ED Visit is after Visit 9, do not conduct MRI.
Laboratory Tests and Sample Collections														On dosing days, collect samples before dosing.	
Hematology	X					X			X			X	X	X	
Clinical Chemistry	X	X	X	X	X	X	X	X	X	X	X	X	X	X	
Lipid panel	X	X	X	X	X	X	X	X	X	X	X	X	X	X	Includes non-HDL-C.
Coagulation panel	X	X	X	X	X	X	X	X	X	X	X	X	X	X	
ApoB, ApoA-I, ApoC-III	X	X	X	X	X	X	X	X	X	X	X	X	X	X	
ANGPTL3 and ANGPTL3/8	X	X	X	X	X	X	X	X	X	X	X	X	X	X	
TSH	X														
HbA1c	X	X				X			X			X	X		
Insulin		X				X			X			X	X		
Urinalysis	X					X			X			X	X	X	
UACR	X					X			X			X	X	X	Urinary albumin/creatinine ratio calculation.

Study J3F-MC- EZCB(e)	Screen ing	Double-Blind Treatment and Assessment											Follow- up	Comments	
				X	X	X		X	X		X	X			
Remote Visits			X	X	X		X	X		X	X				V801 on-site for all sites including the US
Visits	1	2	3	4	5	6	7	8	9	10	11	12	ED	801	ED = early discontinuation.
Days from randomization	-45	0	15	30	60	90	120	150	180	210	240	270	—	360	
Visit interval tolerance (days)		—	±3	±3	±3	-5 to +10	±7	±7	±7	±7	±7	±7	—	±7	Visit 1 procedures may be conducted over more than 1 day if all activities are completed within the allowable visit tolerance.
Fasting Visit	X	X	X	X	X	X	X	X	X	X	X	X	X	X	Participants should not eat or drink anything but water for 8 hours before the visit. If a participant arrives not fasted, schedule the laboratory draw for another date.
Serum pregnancy	X														Only for WOCBP and women with a history of tubal ligation. See Section 10.4.
Urine pregnancy (local)		X				X			X			X	X		Collect for WOCBP only. This test must be performed at Visits 2, 6, 9, and end of study with the result available prior to first dose of intervention. Perform additional pregnancy tests if a menstrual period is missed, if there is clinical suspicion of pregnancy, or as required by local law or regulation.
FSH	X														Optional. Perform as needed to confirm postmenopausal status. See Section 10.4.
Hepatitis B virus (HBV)	X														
Hepatitis C virus (HCV)	X														
HIV	X														
Estimated glomerular filtration rate (eGFR)	X	X		X		X			X			X	X	X	Calculated using the Chronic Kidney Disease Epidemiology Collaboration (CKD-EPI) method.

Study J3F-MC- EZCB(e)	Screening	Double-Blind Treatment and Assessment											Follow-up	Comments	
Remote Visits			X	X	X		X	X		X	X				V801 on-site for all sites including the US
Visits	1	2	3	4	5	6	7	8	9	10	11	12	ED	801	ED = early discontinuation.
Days from randomization	-45	0	15	30	60	90	120	150	180	210	240	270	—	360	
Visit interval tolerance (days)		—	±3	±3	±3	-5 to +10	±7	±7	±7	±7	±7	±7	—	±7	Visit 1 procedures may be conducted over more than 1 day if all activities are completed within the allowable visit tolerance.
Fasting Visit	X	X	X	X	X	X	X	X	X	X	X	X	X	X	Participants should not eat or drink anything but water for 8 hours before the visit. If a participant arrives not fasted, schedule the laboratory draw for another date.
Pharmacokinetic (PK) samples		X				X									Visit 2: Collect 2 samples. First sample at 0.5 hr post-dose, and Second sample: 4-12 hr post-dose (minimum 2 hr). Visit 6: Collect 1 sample any time on the next day after 2nd injection, 24-48 hrs post-dose. This may require a PK-specific visit.
Immunogenicity (ADA)		X	X	X		X			X			X	X	X	Collect samples before dosing. If an immediate or nonimmediate systemic drug hypersensitivity reaction occurs, collect an additional unscheduled sample as detailed in Section 10.2.1.
PK sample for immunogenicity		X	X	X		X			X			X	X	X	Collect a time-matched PK sample for all scheduled and unscheduled immunogenicity samples. Collect samples before dosing.
High-sensitivity C-reactive protein (hsCRP)		X				X			X			X	X	X	
Stored Samples															On dosing days, collect samples before dosing.
Genetic sample		X													

Study J3F-MC- EZCB(e)	Screening	Double-Blind Treatment and Assessment											Follow-up	Comments	
		1	2	3	4	5	6	7	8	9	10	11			12
Remote Visits			X	X	X		X	X		X	X				V801 on-site for all sites including the US
Visits	1	2	3	4	5	6	7	8	9	10	11	12	ED	801	ED = early discontinuation.
Days from randomization	-45	0	15	30	60	90	120	150	180	210	240	270	—	360	
Visit interval tolerance (days)		—	±3	±3	±3	-5 to +10	±7	±7	±7	±7	±7	±7	—	±7	Visit 1 procedures may be conducted over more than 1 day if all activities are completed within the allowable visit tolerance.
Fasting Visit	X	X	X	X	X	X	X	X	X	X	X	X	X	X	Participants should not eat or drink anything but water for 8 hours before the visit. If a participant arrives not fasted, schedule the laboratory draw for another date.
Exploratory biomarker samples		X		X		X			X			X	X		
Randomization and Dosing using IWRS															
Register visit	X	X	X	X	X	X	X	X	X	X	X	X	X	X	
Randomization		X													
Dispense in IWRS		X				X									
Dispense intervention		X				X									
Administer intervention		X				X									

Abbreviations: ANGPTL = angiotensin-like; Apo = apolipoprotein; CV = cardiovascular; ECG = electrocardiogram; FSH = follicle-stimulating hormone; ICF = informed consent form; IWRS = interactive web-response system; MRI = magnetic resonance imaging; TSH = thyroid-stimulating hormone; WOCBP = women of childbearing potential.

2. Introduction

LY3561774

LY3561774 is a novel Dicer-substrate siRNA oligonucleotide designed to reduce the levels of ANGPTL3 protein expression.

How blocking ANGPTL3 reduces lipid levels

Blocking ANGPTL3 activity or preventing its expression is a potential therapeutic approach to reducing ApoB-containing lipoprotein particles that are contributing risk factors for ASCVD (Graham et al. 2017; Stitzel et al. 2017).

Loss-of-function mutations in the ANGPTL3 gene are associated with decreased plasma TGs, LDL-C, and HDL-C levels (Graham et al. 2017; Stitzel et al. 2017). In turn, the reduction of these atherogenic lipids is expected to result in decreased risk of primary and secondary MACE.

LY3561774 clinical development

LY3561774 is being developed as a treatment for patients with mixed dyslipidemia to ultimately reduce the risk of MACE.

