4.1. Overall Design

This is a Phase 2, randomized, double-blind, placebo-controlled, parallel-arm study to investigate the efficacy and safety of LY3561774 in adults with mixed dyslipidemia.

The planned treatment arms are

- 100 mg LY3561774 or placebo
- 400 mg LY3561774 or placebo, and
- 800 mg LY3561774 or placebo.

Intervention administration is by subcutaneous injection.

Dosing will occur twice during the study, on Day 0 and Day 90 (-5 to +10 days).

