Exception: if the participant is on a stable dose for at least 3 months prior to screening and will continue the stable dose during the study.

Prior or concurrent clinical study experience

43. Are currently enrolled or have participated within the last 6 months in a clinical study involving an investigational intervention or any other type of medical research judged not to be scientifically or medically compatible with this study.
44. Have previously completed or withdrawn from this study.

Other exclusions

45. Are breastfeeding.
46. Have an average weekly alcohol intake more than 21 units per week for men and 14 units per week for women or are unwilling to stop alcohol consumption from 48 hours prior to each visit.
1 unit of alcohol is equal to
- 12 ounces or 360 mL of beer
 - 5 ounces or 150 mL of wine, or
 - 1.5 ounces or 45 mL of distilled spirits.
47. Are unwilling to have an MRI scan or have contraindications for MRI scanning
- a. have a cardiac pacemaker or implants made out of metal, for example, cochlea implants, nerve stimulators, magnetic vascular clips, or metallic heart valves
 - b. Have extreme claustrophobia
 - c. Weight or girth exceeds scanner capabilities, or
 - d. In the opinion of the investigator, have any condition or circumstance that would interfere with completion of the MRI.
48. Are Lilly employees or are employees of any third party involved in the study who require exclusion of their employees.
49. Are investigator site personnel directly affiliated with this study and/or their immediate families. Immediate family is defined as a spouse, parent, child, or sibling, whether biological or legally adopted.
50. Are unsuitable for inclusion in the study in the opinion of the investigator.

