6.4. Study Intervention Compliance

Study intervention will be administered under medical supervision by the investigator or designee. The study intervention and study participant identification will be confirmed prior to the time of dosing. The date and time of each dose administered will be recorded in the source documents and in the CRF.

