7.1. Discontinuation of Study Intervention

When necessary, a participant may be permanently discontinued from study intervention.

Situations when discontinuation of study intervention may occur

A participant should be permanently discontinued from study intervention if

- the participant becomes pregnant during the study
- a prohibited treatment listed in Section 10.7.3 is initiated during the study, or
- in the opinion of the investigator, the participant should permanently discontinue the study intervention for safety reasons.

If the investigator determines that a systemic hypersensitivity reaction has occurred related to study intervention administration, the participant may be permanently discontinued from the study intervention, and the sponsor's designated medical monitor should be notified. If the investigator is uncertain about whether a systemic hypersensitivity reaction has occurred and whether discontinuation of study intervention is warranted, the investigator should consult the sponsor.

If study intervention is permanently discontinued, the participant will remain in the study and follow procedures for the remaining study visits as shown in the SoA.

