8.2.7. Pregnancy Testing

Pregnancy testing will occur throughout the duration of the study as outlined in the SoA.

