Any post-study pregnancy-related SAE considered reasonably related to the study intervention by the investigator will be reported to the sponsor as described in Section 8.3.1. While the investigator is not obligated to actively seek this information in former study participants, he or she may learn of an SAE through spontaneous reporting.

Any female participant who becomes pregnant while participating in the study will be withdrawn from the study. If the participant is discontinued from the study, follow the standard discontinuation process and continue directly to the follow-up phase. The follow-up on the pregnancy outcome should continue independent of intervention or study discontinuation.

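### The urine pregnancy result is required only before the first dose, so the second and last dose can be given with the Visit 6 result unread

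*Protocol*

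**What the plan says.** The urine pregnancy row of the Schedule of Activities (Protocol 1.3) marks a local test at Visits 2, 6, 9 and 12 and at early discontinuation, for women of childbearing potential only. Its comment says: "This test must be performed at Visits 2, 6, 9, and end of study with the result available prior to first dose of intervention". The same comment asks for extra tests after a missed period, on clinical suspicion, or where local rules require them.

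The dosing rows of the same table mark administration at Visits 2 and 6 only. Section 4.1 sets these at Day 0 and Day 90, with a window of 5 days before to 10 days after for the second dose. The header over the laboratory rows says: "On dosing days, collect samples before dosing".

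Section 7.1 lists among the reasons for permanent discontinuation of study intervention that "the participant becomes pregnant during the study". Section 8.3.2 adds: "Any female participant who becomes pregnant while participating in the study will be withdrawn from the study".

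**The concern.** Once the first dose has been given, the pregnancy rule in Section 7.1 has one practical use: to hold back dose 2. The test that could trigger it is scheduled at the right visit, but the comment ties availability of the result to the first dose only. A site that followed the text exactly could collect urine at Visit 6, inject, and read the result afterwards. A positive result would still lead to withdrawal under Section 8.3.2, but no dose would remain to withhold and the injection could not be undone.

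The drug is long-acting in its effect. Section 2.2 reports that lowering of ANGPTL3, triglycerides and LDL-C in Phase 1 lasted to the final sample at Day 169. That is pharmacodynamic effect and not evidence of harm, and the documents report no reproductive-toxicity finding. Still, women are eligible from age 18 (Section 5.1), and the sponsor's own rules treat pregnancy as a reason to stop. The schedule should allow those rules to work.

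**Working it through.** This is mainly a reading check; the SAP is silent on the point and the plan gives no figure to reproduce.

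**Does any other text require the Visit 6 result before dose 2?**

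- Protocol 1.3, laboratory header: "On dosing days, collect samples before dosing". This fixes the order of collection. The pregnancy comment speaks separately of the result being available, so collection and result are distinct requirements.
- Section 8.2.7: "Pregnancy testing will occur throughout the duration of the study as outlined in the SoA". It points back to the schedule and adds no rule.
- Section 6.4: "The study intervention and study participant identification will be confirmed prior to the time of dosing". The pregnancy result is not among the items confirmed.
- Section 5.2: the exclusions include "Are breastfeeding" but not pregnancy. In any case, eligibility is confirmed at Visits 1 and 2, not at Visit 6.
- Section 10.4.2: non-abstinent women must take pregnancy tests, with no link to dosing.
- Section 10.8: checking for a negative urine test is listed as a telemedicine task in exceptional circumstances, again with no link to dosing.

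None does. Two doses are planned, the result is required before one, and that one is not the dose the Section 7.1 stop can still prevent.

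**Age of the newest scheduled result if Visit 6 is unread.** Visit 2 is Day 0. Visit 6 falls between 90 − 5 = Day 85 and 90 + 10 = Day 100. No urine pregnancy test is scheduled at Visits 3, 4 or 5. The newest routinely scheduled result is therefore 85 to 100 days old. A woman who misses a period or is suspected to be pregnant should have a more recent test.

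**Number of women concerned.** The documents give no count, so a share of 5% to 20% of the 175 randomized participants is assumed. The share on active drug in the 2:1:2:2 allocation is (1 + 2 + 2)/7 = 5/7.

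| Assumed share | Women of childbearing potential | On LY3561774 (× 5/7) |
|---|---|---|
| 5% | 175 × 0.05 = 8.75 | 6.25 |
| 20% | 175 × 0.20 = 35 | 25 |

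**Rough ceiling on pregnancies by Visit 6.** Section 10.4.2 defines highly effective contraception as a failure rate below 1%, without stating a period. Taking the upper row and assuming that contraception performs as rated:

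- 1% per year: 35 × 0.01 × 100/365 = 0.096 in all, and 25 × 0.01 × 100/365 = 0.068 on active drug.
- 1% over the whole interval: 35 × 0.01 = 0.35 in all, and 25 × 0.01 = 0.25 on active drug.

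These count pregnancies, not pregnancies that would also go unread at dosing, so the expected number of avoidable exposures is lower still.

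**The case against.** The strongest reply is that failure needs an unlikely chain of events. The Visit 6 test is mandatory, the sample precedes dosing, Visit 6 is not among the visits marked as remote, dosing is medically supervised, and pregnancy is a listed stopping reason. A site would have to take the urine, inject without looking, and then find a positive. Most sites would probably read a local test in time. Missed-period testing would catch many earlier conceptions, which limits what the 85-to-100-day figure means for menstruating women. The expected number of pregnancies is well below one. A woman who conceived before Day 90 may also already be under the effect of dose 1, so withholding dose 2 avoids further exposure, not all exposure.

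All of this stands as an argument about size. It does not supply the missing rule, because the protocol states a condition on the result and limits it to the wrong dose for this purpose. Reliance on good practice is also weaker here than usual. Under Section 6.3 an unblinded third party prepares and gives the injection and has no other study role, so the person injecting may not be the person who reads the test. In exceptional circumstances, Section 10.8 also lets dosing move to a mobile visit or another location.

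Two supporting points carry little weight: Section 6.4 deals with compliance and is not a safety checklist, and the breastfeeding exclusion concerns entry to the study. The conclusion does not depend on either.

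**Conclusion.** The concern holds. As written, the protocol permits the only dose that the Section 7.1 pregnancy rule can still withhold to be given before the pregnancy result is known. The gap is confined to women of childbearing potential at Visit 6. Its absolute size is small: under the assumptions above, fewer than 0.1 to 0.35 pregnancies by Visit 6 at the upper end of the range, before allowing for the chance that a site reads the test anyway. The headcount rests on an assumed 5% to 20% share, and the pregnancy ceiling on contraception working at the rate Section 10.4.2 states. The reading of the text needs neither assumption. The point has no bearing on the primary analysis. It is a participant-safety correction that should be made, not a threat to the trial's validity.

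**What to change.** In the urine pregnancy comment of Protocol 1.3, replace the condition on the first dose with: *a negative result must be available before dosing at Visit 2 and before dosing at Visit 6*. The Visit 9 and end-of-study tests need no dosing condition, and nothing else in the schedule changes.

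The cost is one sentence. The test is already scheduled at Visit 6, so there is no added sample, visit or procedure. Section 10.2 says only that the test is done locally and gives no turnaround time. Where a site uses an on-the-spot test, it simply reads the result before injecting. Where it sends the sample to a local laboratory, the injection would wait for the result, and the window to Day 100 leaves some room for that.
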